Study Drug Administration	
X
 
Part A/B: Day 1 Cycle 1: SC dose Day 1 Cycle ≥ 2: IV dosing
 
Part C: Day 1 of each cycle: SC dosing manually by syringe
 
Part D: Day 1 of each cycle: SC dosing manually by syringe
		
The first dose must be administered within 3 calendar days following treatment assignment/randomization.^c For Parts A-D, drug administration must occur on Day 1 of Cycle 1 and Cycle 2. For Cycle 3 and beyond, drug administration is ± 3 days but no less than 21 days from the previous dose. Study drug infusion start and stop times will be recorded for SC and IV administration.
 
Part A and Part B All assigned/randomized participants receive SC nivolumab (BMS-986298) on Cycle 1 Day 1. On Day 1 of Cycle 2 and each cycle thereafter, all participants in treatment Groups 1, 2, 3, and 4 receive IV nivolumab (BMS-936558) every 4 weeks (Q4W).

Table 2-3: On-treatment Procedural Outline (CA2098KX) - Parts A-E

Procedure	Parts A-D: Day 1 of each treatment cycle (Cycle = 28 days) Part E: [REDACTED] of each treatment cycle^a (Cycle = 28 days)	Timepoints Relative to Dosing Schedule	Notes ^b
	Part E: [REDACTED] of each cycle: SC dosing manually by syringe		
Part C Upon approval of revised protocol 03, Participants in Part A and Part B will cross over to Part C to receive 1200 mg SC nivolumab (BMS-986298) with rHuPH20 manually by syringe on Day 1 of each treatment cycle.
 
Part D All assigned participants in Group 5 receive SC nivolumab (BMS-986298) with rHuPH20 manually by syringe on Day 1 of each cycle.
 
Part E All assigned participants in Group 6 receive 600 mg SC nivolumab (BMS-986298) coformulated with rHuPH20 manually by syringe on [REDACTED] of each cycle. For Part E, participants may be dosed [REDACTED] from the previous dose.
 
All participants in the study will be treated for a maximum of 104 weeks total (nivolumab IV or/and SC) or until confirmed progression, unacceptable toxicity, withdrawal of informed consent, or discontinuation of the study by the Sponsor. Treatment for all participants can continue beyond initial investigator-assessed progression until a maximum of 104 weeks total (nivolumab IV or/and SC) (see Section 8.1.2).

Table 2-3: On-treatment Procedural Outline (CA2098KX) - Parts A-E

Procedure	Parts A-D: Day 1 of each treatment cycle (Cycle = 28 days) Part E: [REDACTED] of each treatment cycle ^a (Cycle = 28 days)	Timepoints Relative to Dosing Schedule	Notes ^b
Outcomes Research Assessments			
Patient Experience and Preference Questionnaire	See Section 9.10.1 for further details.		
Qualitative Patient Interviews	See Section 9.10.2 for further details.		

Abbreviations: AE = adverse event; aPTT = activated partial thromboplastin time; BMS = Bristol-Myers Squibb; COVID-19 = coronavirus disease 2019; CRF = case report form; CT = computed tomography; ECOG = Eastern Cooperative Oncology Group; HCC = hepatocellular carcinoma; HCG = human chorionic gonadotropin; IgG = immunoglobulin G; INR = international normalized ratio; IV = intravenous; MRI = magnetic resonance imaging; NCI CTCAE v.5 = National Cancer Institute Common Terminology Criteria for Adverse Events version 5; PT = prothrombin time; Q4W = every 4 weeks; rHuPH20 = recombinant human hyaluronidase PH20; SAE = serious adverse event; SARS-CoV-2 = severe acute respiratory syndrome coronavirus disease 2; SC = subcutaneous; WOCBP = women of childbearing potential.

- ^a If a dose is delayed, the procedures schedule for that same time point must also be delayed to coincide with when that time point's dosing actually occurs, with the exception of tumor assessments which must occur as scheduled.
- ^b Some of the assessments referred to in this section may not be captured as data in the CRF. They are intended to be used as safety monitoring by the treating physician. Additional testing or assessments may be performed as clinically necessary or where required by institutional or local regulations and should be documented in the patient's source notes.
- ^c Randomization/treatment assignment = randomization (Part B Groups 2, 4) /treatment assignment (Part A, Part B Group 3, Parts C, D, and E).

Table 2-4: Safety Follow Up Procedural Outline (CA2098KX) - Parts A-E

Procedure	Follow-up Visit 1 and Visit 2	Survival Follow-up	Notes ^a
			
Follow-up Visit 1 = 30 days from last dose \pm7 days, or may be on date of discontinuation if the date of discontinuation is more than 30 days after last dose.
 
Follow-up Visit 2 = approximately 100 days (\pm 7 days) from last dose.

Targeted Physical Examination	X		Weight, BP, HR, temperature, ECOG performance status
Vital Signs	X		See note in screening procedures.
Serious and Non-serious Adverse Event Assessment	X	X*	
*Beyond 100 days from the last dose of study therapy, participants will be followed for drug-related AEs until AE resolves, returns to baseline, or is deemed irreversible, or until the participant is lost to follow-up or withdraws study consent.
 
All AEs (SAEs and non-serious AEs) associated with confirmed or suspected SARS-CoV-2 infection will be followed until resolution, the condition stabilizes, or is deemed irreversible, or until the participant is lost to follow-up (as defined in Section 8.3). For suspected cases, participants should be followed until SARS-CoV-2 infection is ruled out as per institutional policy on SARS-CoV-2.
 
COVID-19 or positive SARS-CoV-2 test results should be reported to BMS within 24 hours regardless of the seriousness criteria.

Laboratory Tests	X		
To be performed at Follow-up Visit 1, repeat at Follow-up Visit 2 if study drug-related toxicity persists.
 
See Section 9.4.4.

Review of Concomitant Medications	X		
Subsequent Cancer Therapy	X	X	Include documentation of subsequent cancer therapy (ie, systemic therapy, tumor-directed surgery, or radiation therapy).
Pregnancy Test	X		Serum or urine

Table 2-4: Safety Follow Up Procedural Outline (CA2098KX) - Parts A-E

Body Imaging	X	X	Participants who discontinue treatment for reasons other than tumor progression should continue to have tumor assessments: contrast-enhanced CT of the chest, CT/MRI of the abdomen, pelvis, and all other known and/or suspected sites of disease should occur every 12 weeks (± 1 week) until investigator-assessed disease progression or withdrawal of consent, whichever occurs first. Radiographic assessments should not be delayed until follow-up Visit 1 or Visit 2. See Section 9.1.1.1 for further details on imaging assessments.
Brain Imaging	X	X	Participants with a history of brain metastasis or symptoms should have surveillance MRIs per standard of care (approximately every 12 weeks) or sooner if clinically indicated.
Collection of Survival Information		X	Every 3 months (± 14 days) from Follow-up Visit 2 until death, lost to follow-up, or withdrawal of study consent for up to 5 years following start of therapy. May be performed by phone contact or office visit. BMS may request that survival data be collected on all treated participants outside of the 3-month specified window. At the time of this request, each participant will be contacted to determine their survival status unless the participant has withdrawn consent for all contact.
PK and Immunogenicity Blood Sampling	X		
Biomarker Assessment			

Abbreviations: AE = adverse event; BMS = Bristol-Myers Squibb; BP = blood pressure; CRF = case report form; COVID-19 = coronavirus disease 2019; CT = computed tomography; ECOG = Eastern Cooperative Oncology Group; HR = heart rate; MRI = magnetic resonance imaging; PK = pharmacokinetics; SAE = serious adverse event; SARS-CoV-2 = severe acute respiratory syndrome coronavirus 2.

^a Some of the assessments referred to in this section may not be captured as data in the CRF. They are intended to be used as safety monitoring by the treating physician. Additional testing or assessments may be performed as clinically necessary or where required by institutional or local regulation and should be documented in the patient's source notes.

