To characterize biomarker measures [REDACTED]	
• Including, but not limited to: summary measures of change (or % change) from baseline in various biomarkers and molecular characteristics of the tumor (Parts A-D, and based on tissue availability for Part E)/blood
To assess the immunogenicity of rHuPH20	
• Incidence of anti-rHuPH20 antibodies and neutralizing antibodies, if applicable
To assess the preliminary participant experience and preference for SC or IV administration of nivolumab.	
• Patient experience and preference questionnaire• Qualitative Patient Interviews

Abbreviations: AE = adverse event; AUC(TAU) = area under the concentration-time curve over the dosing interval; Cmax = maximum observed serum nivolumab concentration; Ctau = observed serum nivolumab concentration at the end of the dosing interval; Ctrough = trough observed serum nivolumab concentration; IV = intravenous; MedDRA = Medical Dictionary for Regulatory Activities; ORR= objective response rate; OS = overall survival; PFS = progression-free survival; Q2W = every 2 weeks; rHuPH20 = recombinant human hyaluronidase PH20; SAE = serious adverse event; SC = subcutaneous; SMQ = standardized MedDRA queries; TRAE = treatment-related adverse event; TRSAE = treatment-related serious adverse event.

Overall Design:

Study CA2098KX is a multicenter, randomized, open-label, multi-tumor Phase 1/2 study that will evaluate the PK, safety, and tolerability of nivolumab administered subcutaneously with and without rHuPH20 in participants with 1 of the following advanced or metastatic tumor types: non-small cell lung cancer (NSCLC); renal cell carcinoma (RCC); unresectable or metastatic melanoma; hepatocellular carcinoma (HCC); or colorectal cancer (CRC) (microsatellite instability-high [MSI-H] or mismatch repair deficient [dMMR]). For Part B only, addition of other solid tumors were considered, where nivolumab PK was well characterized and discussed with the Sponsor. In addition to the above tumors, Part E will also include participants with metastatic urothelial carcinoma (mUC). The study is divided into the following periods: a Screening period; a Treatment period consisting of Part A, Part B, Part C, Part D, and Part E; and a Safety Follow-up period.

Figure 1: CA2098KX Study Schematic^a

Parts C, D and E: Treatment until 104 weeks total, withdrawal, toxicity, RECIST v1.1 progression, or death

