2 SCHEDULE OF ACTIVITIES

Table 2-1: Screening Procedural Outline (CA2098KX) - Parts A-D

Procedure	Screening Visit	Notes
Screening assessments must be performed within 28 days prior to the first dose in the study.		
Eligibility Assessments		
Informed Consent	X	A participant is considered enrolled only when a protocol-specific informed consent is signed.
Inclusion/Exclusion Criteria	X	All inclusion/exclusion criteria should be assessed and confirmed prior to first dose. See Sections 6.1 and 6.2 .
Medical History	X	Include any toxicities or allergy related to previous treatments including prior anticancer/radiotherapy, smoking history (including electronic cigarettes), and alcohol history.
ECOG	X	Within 14 days prior to first dose. See Appendix 7 .
Register participant in IRT	X	IRT contact must occur for IVRS participant number assignment at the time when informed consent is obtained.
Microsatellite instability and mismatch repair status	X	Confirm documentation of prior local testing (high microsatellite instability [MSI-H] and/or mismatch repair deficient [dMMR]) for participants with colorectal cancer (CRC).
Tumor Tissue Sample	X	
Sufficient tumor tissue obtained up to 12 months prior to first study treatment in the metastatic setting or from an unresectable site (block [REDACTED] is requested, obtained from core needle biopsy, excisional, or incisional biopsy). For fresh samples, the tumor should be amenable to biopsy and the lesion should be distinct from target lesions being evaluated for radiologic response, and the same lesion should be used for both the baseline and on-treatment sampling. Participants should not have received any systemic anticancer therapy after the date that the submitted tumor tissue was obtained. Up to 5 participants from each part of the trial (part A & B) and approximately 15 participants in Part D, who do not meet tissue requirements may be allowed treatment after discussion with the Medical Monitor.
 
[REDACTED]
 
Assessment of tumor-cell PD-L1 expression by IHC must be performed centrally using pre-treatment tissue sample. [REDACTED] must be collected for all participants in Part A prior to initiation of Part B. For participants with CRC, assessment of tumor PD-L1 expression is not required, since documentation of MSI-H/dMMR status is required.

Table 2-1: Screening Procedural Outline (CA2098KX) - Parts A-D

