Tumor Sample Submission	See Notes	Tumor tissue sample submission is highly recommended, but optional for participants in Part E. For all participants in Part E, including mUC participants, submission of an archival FFPE tissue block (preferred) or unstained slides of tumor tissue from core biopsy, excisional biopsy, or surgical specimen obtained within 12 months of enrollment is highly recommended. For fresh samples, the tumor should be amenable to biopsy and the lesion should be distinct from target lesions being evaluated for radiologic response, and the same lesion should be used for both the baseline and on-treatment sampling. Fine needle aspirates or other cytology samples are not acceptable. Tumor PD-L1 expression by IHC is an optional assessment for participants in Part E. [REDACTED] Please refer to Section 9.8 for additional information.
Baseline Tumor Assessment	X	Must be performed within 28 days prior to the first dose of study drug. Contrast-enhanced CT of the chest, CT/MRI of the abdomen, pelvis, and all other known and/or suspected sites of disease. See Section 9.1.1.1 . MRI of the brain without and with contrast is required for participants with known or suspected brain metastases, unless participant has completed an imaging study of the brain within 28 days of study drug administration. CT of the brain (with and without contrast) can be performed if MRI is contraindicated. See Section 9.1.1.1 .
Disease Assessments	X	For participants with HCC only: serum alpha fetoprotein (AFP)

Table 2-2: Screening Procedural Outline (CA2098KX) - Part E

Procedure	Screening Visit	Notes ^a Screening assessments must be performed within 28 days prior to the first dose in the study.
Safety Assessments		
Assessment of Signs and Symptoms	X	Within 14 days prior to the first dose of study drug.
Physical Examination, Measurements, Vital Signs, and Performance Status	X	Height, weight, performance status (Appendix 7), BP, HR, temperature and oxygen saturation by pulse oximetry at screening only. Must be collected within 14 days prior to the first dose of study drug.
Concomitant Medication Collection	X	Within 14 days prior to the first dose of study drug. Vaccine use within 30 days prior to first study treatment. See Section 6.2 .
Electrocardiogram (ECG)	X	At rest. Within 14 days prior to the first dose of study drug.

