 - (5) Prothrombin International normalized ratio (INR) ≤ 2.3 or prothrombin time (PT) ≤ 6 seconds above control
 - (6) Albumin ≥ 2.8 g/dL
 - (7) Participants with chronic hepatitis B virus (HBV) infection must be on antiviral therapy and must have HBV DNA < 500 IU/mL.
 - (8) Platelets $\geq 60 \times 10^3/\mu\text{L}$
- v) **Parts A-E: Colorectal cancer, metastatic (MSI-H or dMMR):**
 - (1) MSI-H or dMMR CRC that has progressed following treatment with a fluoropyrimidine, oxaliplatin, and irinotecan.
- vi) **Part B only:** other solid tumor types were permitted where PK was well characterized and discussed with the Sponsor.
- vii) **Part E only:** Metastatic urothelial carcinoma:
 - (1) Participants with metastatic or locally advanced (cT4b, or any N+ [N1-N3], or any M1) urothelial carcinoma (including mixed histology with elements of other subtypes) of the renal pelvis, ureter, bladder, or urethra.
 - (2) Participants must have progression
 - (a) After treatment with at least 1 platinum-based chemotherapy regimen for metastatic or locally advanced disease

OR

 - (b) Within 12 months of neoadjuvant or adjuvant platinum-based chemotherapy.
- b) Measurable disease as per RECIST version 1.1 criteria (see [Appendix 5](#) for criteria)
- c) Participants must have an ECOG performance status of 0 or 1 (see [Appendix 7](#) for ECOG Performance Status scales).
- d) All participants must have the ability to comply with treatment, patient-reported outcomes, PK, pharmacodynamic sample collection, and study follow-up requirements.
- e) Prior radiotherapy must have been completed at least 2 weeks prior to study treatment administration.

f) Screening laboratory values must meet the following criteria (using CTCAE v.5). The laboratory values for platelets, AST/ALT, and total bilirubin are adjusted for participants with HCC and are defined under Inclusion Criteria 2, Letter a, iv.

- i) White blood cell (WBC) count $\geq 2000/\mu\text{L}$
- ii) Neutrophils $\geq 1500/\mu\text{L}$
- iii) Platelets $\geq 100 \times 10^3/\mu\text{L}$
- iv) Hemoglobin $\geq 9.0 \text{ g/dL}$
- v) Serum creatinine $\leq 1.5 \times$ upper limit of normal (ULN) or calculated creatinine clearance (CrCL) $> 40 \text{ mL/min}$ (using the Cockcroft Gault formula):
$$\text{Female CrCL} = \frac{(140 - \text{age in years}) \times \text{weight in kg} \times 0.85}{72 \times \text{serum creatinine in mg/dL}}$$

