9.8.1 Tumor Tissue Specimens

For Part A, the Cycle 1 Day 15 tumor biopsy is highly recommended but optional. For Part B and Part D, participants will be required to undergo on-treatment biopsy unless judged as posing unacceptable risk by the investigator. Sufficient, recent tumor tissue FFPE block from a metastatic tumor lesion or from an unresectable primary tumor lesion, which has not been previously irradiated, must be submitted. If a participant had a biopsy in the preceding 12 months, participants can be enrolled without needing a repeat biopsy after discussion with the Medical Monitor and availability of FFPE blocks [REDACTED] as delineated below. For Part E, screening and on-treatment tumor biopsies are highly recommended, but optional.

- 1) **Parts A-D only:** Pre-treatment tissue must be collected and locally confirmed for adequate tissue quantity and quality during the screening period prior to first dose of study treatment and then sent to the central laboratory for testing. Please refer to lab manual for detailed biopsy collection instructions. Up to 5 participants from each part of the trial (Part A and B) who do not meet tissue requirements may be allowed treatment after discussion with the Medical Monitor. Other exceptions may be provided at the discretion of the Medical Monitor.
 - a) Approximately 15 participants in Part D, who do not meet tissue requirements may be allowed treatment after discussion with the Medical Monitor.
 - b) Participants should not have received any systemic anticancer therapy after the date that the submitted tumor tissue was obtained. Exceptions may be made with Medical Monitor approval in cases where fresh tumor tissue or recent tumor tissue are inaccessible.
- 2) **Part E:** Tumor tissue collection is highly recommended, but optional. For all participants in Part E, including mUC participants, submission of an archival FFPE tissue block (preferred) or unstained slides of tumor tissue from core biopsy, excisional biopsy, or surgical specimen obtained within 12 months of enrollment is highly recommended.

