10.3.6 Biomarker Analyses

Descriptive summary statistics of biomarker assessments will be presented at baseline and at each on-study time point described in [Section 9.8](#), [Table 9.8-1](#), and [Table 9.8-2](#), unless otherwise specified.

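### Part E can take tumour tissue from before the last systemic therapy as its biomarker baseline, so some tissue change-from-baseline values can include the effect of that therapy (minor, exploratory endpoint)

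*Combined protocol and SAP*

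**What the plan says.** **Parts A-D.** Table 2-1 carries this condition on baseline tissue: "Participants should not have received any systemic anticancer therapy after the date that the submitted tumor tissue was obtained". It appears again in the Parts A-D text of Section 5.1.1, in inclusion criterion 2(h), and in Section 9.8.1 item 1(b), which stands under an item limited to Parts A-D. Item 1(b) also allows departures: "Exceptions may be made with Medical Monitor approval in cases where fresh tumor tissue or recent tumor tissue are inaccessible".

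**Part E.** Table 2-2 says: "Tumor tissue sample submission is highly recommended, but optional for participants in Part E". It names the material it would like to receive: "submission of an archival FFPE tissue block (preferred) or unstained slides of tumor tissue from core biopsy, excisional biopsy, or surgical specimen obtained". The preferred form is thus an archival block, and the only timing condition is the age of the tissue: "surgical specimen obtained within 12 months of enrollment is highly recommended". Section 5.1.1 (Part E) and Section 9.8.1 item 2 say the same. For fresh samples, Table 2-2 asks that the same lesion supply both the baseline and the on-treatment sample. Table 9.8-2 schedules tumour biopsies at screening and Cycle 1 Day 15, both optional.

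**Endpoint and analysis.** The exploratory biomarker endpoint is change or percent change from baseline, covering "molecular characteristics of the tumor (Parts A-D, and based on tissue availability for Part E)/blood". Section 9.8 states that pre- and on-treatment samples will serve to characterise the pharmacodynamic activity of SC nivolumab. Section 10.3.6 says: "Descriptive summary statistics of biomarker assessments will be presented at baseline and at each on-study time point". It does not define the tumour baseline and does not mention tissue date.

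**The concern.** A pharmacodynamic reading of tumour change needs a baseline that shows the tumour shortly before the first nivolumab dose. If the baseline block was taken before a course of chemotherapy or targeted therapy, the Day 15 difference covers that therapy and the intervening disease course as well as two weeks of SC nivolumab. PD-L1 expression and tumour-infiltrating lymphocytes, the tissue markers named in Section 9.8, could have moved before nivolumab was given. The Parts A-D condition guards against this. Without it, a shift in Part E tissue markers could not be attributed to SC nivolumab in the affected pairs, and Part E results would be hard to set beside those of the other Parts.

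**Working it through.** The documents give no figure to reproduce, so the check is a comparison of texts followed by an illustrative size.

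**Step 1. Where the condition appears.**
- Parts A-D: Table 2-1, Section 5.1.1, criterion 2(h) and Section 9.8.1 item 1(b). Four places, all limited to Parts A-D.
- Part E: Table 2-2, Section 5.1.1 (Part E), the Part E sub-item of criterion 2(h), which refers on to 9.8.1, and Section 9.8.1 item 2. None of the readable text contains it. Table 2-2 and Section 5.1.1 have redactions near the Part E tissue wording; Section 9.8.1 item 2 shows none.

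**Step 2. Which Part E participants have had earlier systemic therapy (Section 6.1).**
- NSCLC: a prior platinum doublet.
- RCC: one or two prior anti-angiogenic regimens.
- HCC: prior sorafenib or lenvatinib.
- CRC: prior fluoropyrimidine, oxaliplatin and irinotecan.
- mUC: "After treatment with at least 1 platinum-based chemotherapy regimen for metastatic or locally advanced disease", or progression within 12 months of neoadjuvant or adjuvant platinum.
- Melanoma: previously untreated, except that adjuvant BRAF/MEK-targeted therapy is allowed.

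Five of six tumour types are therefore pretreated by eligibility. This counts types, not participants. The only planned Part E count by tumour type is about 10 of 36 with mUC (10/36 = 28%).

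**Step 3. Can a pre-therapy block fall inside the 12-month limit?** Yes. Take the adjuvant mUC route: a surgical specimen, then adjuvant platinum, then progression and enrolment, all within 12 months. The specimen satisfies Table 2-2 and pre-dates the platinum.

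**Step 4. Which pairs are affected.** Only those whose baseline is an archival sample taken before the last systemic therapy. Pairs with a fresh screening biopsy, pairs with a post-therapy block, and melanoma pairs without prior adjuvant therapy are not.

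**Step 5. Size.** Let f be the share of Part E pairs that are affected and d the shift that the intervening therapy caused in the marker, in SD. Then

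observed mean change = nivolumab effect + f × d.

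The documents give neither f nor d; f can be anything from 0 to near 1. All values below are assumptions.
- f = 0: bias 0, whatever d is.
- f = 0.25, d = 0.25: 0.25 × 0.25 = 0.06 SD.
- f = 0.5, d = 0.5: 0.5 × 0.5 = 0.25 SD.
- f = 0.75, d = 0.75: 0.75 × 0.75 = 0.56 SD.

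For scale, if the SD of change is 1, the standard error of a mean change is 1/√n. With 15 pairs (assumed) it is 1/√15 = 0.26; with 10 pairs it is 1/√10 = 0.32; with all 36 planned participants paired it is 1/√36 = 0.17. The middle case is thus about one standard error at 15 pairs (0.25/0.26). Comparing the two in the same units assumes that the SD of change equals the SD of the marker, which holds when baseline and Day 15 values correlate at 0.5, since SD of change = SD × √(2(1 − r)).

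**The case against.** The strongest case on the other side is that this is a possibility on an endpoint that bears little weight, and that several stronger readings fail. Most of that stands.

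- A reader might infer that Part E change from baseline does include the effect of earlier therapy. The documents support only that it can. A screening biopsy is scheduled and highly recommended, fresh pairs should come from one lesion, and the affected share could be zero.
- A reader might take Parts A-D as fully protected. They are not. The condition there is a recommendation, the Medical Monitor may waive it, and participants who do not meet tissue requirements may be treated (up to 5 in Parts A and B, or 5 in each by some passages, and about 15 in Part D). The difference is that departures there are exceptions to a stated condition, whereas the readable Part E text states none.
- A reader might object that an excised archival lesion cannot be re-biopsied on Day 15. That is true but not particular to Part E: Parts A-D also accept excisional biopsies up to 12 months old, and the general instruction in Section 9.8.1 item 3 asks for the same lesion only where possible.
- A reader might infer from Section 10.3.6 that different people will be compared at baseline and Day 15. The text does not say so. A change endpoint already implies pairs, and Section 10.3 leaves participant selection and missing data to a SAP whose text is not reproduced in the combined document.
- The redactions near the Part E tissue text mean that the condition's absence from Table 2-2 and Section 5.1.1 cannot be proved. The unredacted item 2 of Section 9.8.1, and the limitation of item 1 to Parts A-D, still point clearly to its absence.

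The Amendment 04 rationale in Appendix 11 explains why Part E tissue is optional. It gives no readable reason for accepting tissue from before the last therapy.

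**Conclusion.** The point holds in limited form. As readable, the plan accepts pre-therapy tissue as the Part E tumour baseline, and Part E contributes to a change-from-baseline endpoint meant to show pharmacodynamic activity. In pretreated tumour types, pairs with an archival block older than the last therapy can therefore carry the effect of that therapy.

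The size cannot be fixed from the documents. It is zero if all baselines are fresh or post-therapy. Under the illustrative assumptions it is 0.06 to 0.56 SD, in either direction.

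Severity is minor. The endpoint is exploratory and descriptive, Part E tissue and PD-L1 testing are optional, and Section 10.3.8 plans no formal comparisons. A reader should not extend the point to the primary PK endpoints, safety or the serum biomarkers, whose baseline is the Cycle 1 Day 1 predose sample.

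**What to change.** In Section 10.3.6 or the SAP, before database lock:

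1. Compare the tissue collection date with the date of the last prior systemic anticancer therapy for every participant with tumour tissue.
2. Base the Part E tumour change-from-baseline summary on within-participant pairs with no intervening systemic therapy. Show other pairs separately and flagged.
3. Report the number of pairs behind each summary.
4. Use older blocks only to describe pre-treatment PD-L1.
5. Apply the same flag to Parts A-D participants treated under the tissue exceptions.

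The cost is analysis-plan wording and a derivation from tissue and prior-therapy dates. No extra biopsy and no change to eligibility or treatment is needed. The downside is fewer Part E pairs in the main tissue summary, from a cohort in which paired tissue is optional.
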